Using the aforementioned published literature, the sponsor anticipates the one-year rate of clinical worsening will be approximately 15% for the population treated with inhaled treprostinil. As such, the sponsor considers the sample size necessary to show a clinically meaningful difference between the esuberaprost and the placebo groups treated with inhaled treprostinil to be prohibitively large. The sponsor intends to restrict recruitment to inhaled treprostinil subjects where an esuberaprost treatment effect will be more readily discerned. Following guidance from the Food and Drug Administration in 2012 (UCM332181) on clinical study enrichment strategies, the inclusion criteria of the current study (protocol, Section 5.2) specified that patients will be randomized into this study only if they are showing signs of deterioration after initial improvement on inhaled treprostinil treatment or have had a clinically suboptimal response to inhaled treprostinil treatment. The specific exclusion of subjects who are likely to be at a lower risk of clinical worsening will reduce the proportion of subjects available for recruitment; however, the targeted study population of those who have shown suboptimal response will be expected to have a higher event rate than would a broader population. Therefore, fewer subjects will be needed to test the hypothesized absolute effect size. Moreover, the target study population is one most likely to benefit from an additional therapy; without additional treatment, approximately 45% of these patients are expected to experience clinical worsening in a year.

Initial start-up activities and recruitment are restricted to ensure the safety of subjects. Therefore, the sample size calculations do not include the initial 6 months of the study to make certain the study has adequate power. The sample size calculations were based on the following assumptions:

- a one-year clinical worsening rate of:
 - 45% in the placebo group (inhaled treprostinil alone)
 - 25% in the esuberaprost group
- proportional hazards over time
- an accrual period of 1.5 years
- total follow-up time of 2.5 years (follow-up time for last subject randomized 1 year; total study duration 2.5 years)
- 0.01 two-sided significance level

[figure not shown]

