This study will randomize approximately 240 subjects (120 subjects per treatment group). Calculation of the sample size was based on the assumptions listed above. Under those assumptions, an exponential maximum likelihood test of equality of survival curves would require 113 events overall to detect a treatment difference at a power of 90% at a 0.01 two-sided significance level. Given the expected accrual period and follow-up time, an appropriate sample size is 240 subjects. There was no restriction or quota with respect to number of subjects by country.

Study sample size is based on a 0.01 two-sided significance level to provide sufficient power to observe ‘substantial evidence’ of effectiveness within a single clinical study. However, at the time of the analysis, the effect will be tested at a significance level of 0.05 (see Section 6.10). The power at a 0.05 two-sided significance level is 97%.

Sample size calculations were performed with nQuery Advisor 7.0 (2014) and PASS (Hintze, 2013) using sample size methods for the log-rank statistic based on Lakatos & Lan (1992).

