6.9 Analysis of Efficacy

All statistical analyses of efficacy will include the stratification variable, baseline inhaled treprostinil use, as a covariate. The sections that describe the analysis of the other secondary outcomes list other planned covariates.

Because the number of subjects in each investigational site is expected to be small, site will not be used as a covariate in the analyses. Moreover, no pooling algorithm will be used.

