6.12.6 First Occurrence Derivation and Analysis

Each subject will be assigned responses for each component of the primary efficacy endpoint. The response will be either the date the event occurred or the date of censoring. Then, the subject will receive one date as the outcome. For subjects who experience at least one of the component outcomes, the event date will be the earliest of the dates of the component outcomes. For those who do not experience any of the outcomes, the date of censoring will be the date of the last study visit.

Prior to unblinding, an addendum will describe in detail the methods to be used to account for missing data in the analysis of the primary outcome.

The TtCW (in days) will be analyzed using the SAS procedure LIFETEST to calculate the log-rank statistic and the associated p-value for testing whether the treatment groups differ. The program will be of the form:

```
proc lifetest data= set plots=survival;
  time TtCW * status(0);
  strata treprostинil_use / group=treatment test=logrank;
  run;
```

The results of the statistical test for the primary study endpoint will be evaluated using a two-sided Type I error rate of 5%. A Cox Proportional Hazards Model (SAS PHREG) will be used to estimate the hazard ratio and its associated 95% confidence interval (CI). This model

will stratify by baseline treprostinil. Graphical displays and tabulations of TtCW will be presented by treatment group.

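### The primary time-to-clinical-worsening analysis is valid but uses only the treprostinil stratum; no analysis adjusted for baseline 6MWD, WHO class and NT-pro-BNP is planned, even as support

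*SAP*

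**What the plan says.** SAP 6.12.6 runs the log-rank test with treprostinil use as the only stratum and estimates the hazard ratio from a Cox model that "will stratify by baseline treprostinil". SAP 6.9 sets the general rule: "All statistical analyses of efficacy will include the stratification variable, baseline inhaled treprostinil use, as a covariate". It leaves further covariates to the sections on the other secondary outcomes.

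The supportive analyses of TtCW (SAP 6.12.7) look at the components. The sensitivity analyses (6.12.8) vary the censoring. None is covariate-adjusted. Baseline 6MWT and WHO class appear for efficacy only as exploratory subgroups (6.15); NT-pro-BNP is not named there.

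The values themselves are collected. WHO class and NT-pro-BNP are taken on Baseline Day 1 before randomization (Protocol 8.2). The two baseline walks follow randomization but precede the first dose (Protocol 4.1, 8.2.1 and Appendix 1). The SAP already adjusts for the baseline value in the models for 6MWT (6.13.1), Borg score (6.14.3) and NT-pro-BNP (6.14.4).

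On size, SAP 4.1 uses a "0.01 two-sided significance level" and requires "113 events overall to detect a treatment difference at a power of 90" percent. At the analysis, "the effect will be tested at a significance level of 0.05". "The power at a 0.05 two-sided significance level is 97" percent.

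**The concern.** When baseline values predict the outcome, a time-to-event comparison that ignores them has less power than one that uses them. Here the values are on hand and are used for three secondary outcomes but not for the endpoint that opens the testing hierarchy.

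The stake is the sponsor's own yardstick. SAP 4.1 sizes the trial at 0.01 so that a single study can carry the evidence of effectiveness, and planned power there is 90%. Reserve is thinner still if the placebo rate is nearer the 30% that Protocol 10.2 also considers. A covariate-adjusted log-rank test keeps the null hypothesis and the planned stratification, so it need not change what is being tested.

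**Working it through.** **1. Reproduce the sizing.** The inputs from SAP 4.1 are 45% and 25% one-year rates, proportional hazards, 1:1 allocation and 113 events.

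- HR = ln(0.75)/ln(0.55) = 0.481, so |ln HR| = 0.7315.
- Schoenfeld events for 90% power at two-sided 0.01: 4 × (2.576 + 1.282)² / 0.7315² = 111.2, rounded up to 112. The plan states 113.
- Power with 113 events: Φ(√113/2 × 0.7315 − z) = Φ(3.888 − z). With z = 2.576 this is 90.5%; with z = 1.960 it is 97.3%. The plan states 90% and 97%.

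The plan's figures reproduce.

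**2. Assume a prognostic strength.** The documents give none. I took the baseline values together to carry a log-hazard SD of 0.3, 0.5 or 0.7, which is a hazard ratio per SD of exp(0.3) = 1.35, exp(0.5) = 1.65 or exp(0.7) = 2.01. I also ran SD 0.

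**3. Simulate the covariate-adjusted log-rank test.** Each trial has 240 subjects, is cut at 113 events, has marginal one-year rates held at the stated values, and has three covariates. There were 4,000 trials per row, without the treprostinil stratum for simplicity. Entries are unadjusted → adjusted power.

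| Scenario | Alpha | SD 0.3 | SD 0.5 | SD 0.7 |
|---|---|---|---|---|
| 45% v 25% | 0.01 | 88.4 → 90.0 | 88.1 → 91.6 | 87.8 → 93.7 |
| 45% v 25% | 0.05 | 96.1 → 96.9 | 96.8 → 97.8 | 96.9 → 98.8 |
| 30% v 17% | 0.01 | 78.6 → 81.0 | 76.4 → 81.4 | 73.1 → 83.1 |
| 30% v 17% | 0.05 | 92.0 → 93.1 | 91.2 → 93.4 | 89.1 → 93.9 |

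The 30% v 17% rows use the weaker alternative in Protocol 10.2 (a 13-point reduction from 30%).

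**4. Repeat.** A second unstratified set of 2,500 trials at 45% v 25% gave gains at 0.01 of 1.4, 3.6 and 4.7 points. A third set of 3,000, with the treprostinil stratum included, gave about 2, 4 and 7 points at 0.01 and 1 to 2 points at 0.05. Simulation error is about 0.4 to 0.7 points per power figure.

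**5. Check the downside.** At SD 0 the two tests gave 89.4% and 89.8% at 0.01, and 97.2% and 97.0% at 0.05, so there is no material difference. Under the null at 0.05, rejection was 5.1-5.8% adjusted and 4.6-5.4% unadjusted (error about 0.35 points). At 0.01 both were 0.9-1.4%.

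**6. Compare with a covariate-adjusted Cox Wald test** (3,000 trials, 45% v 25%, alpha 0.01). With hazard ratio per SD 1.25, power went from 89.1% to 88.7%, so nothing was gained. With 2.0 it went from 87.3% to 94.7%. At 2.0 the adjusted hazard ratio averaged 0.44, against 0.49 unadjusted. The adjusted figure is conditional on the covariates and estimates a different quantity.

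**The case against.** The strongest reply is that nothing is wrong. A log-rank test stratified by the randomization factor is valid, matches the randomization (SAP 3.2.4), is what Protocol 10.1 specifies and fits the log-rank basis of the sizing. That stands in full. A reader might infer that the primary test is in error; the documents do not support that.

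A reader might also infer that the plan is known to give up power. It is not known: prognostic strength is nowhere in the documents, and weak covariates would gain nothing. Nor does the use of walk distance and WHO class in the endpoint prove that their baseline levels predict it. The components use change from baseline. A Class IV subject cannot rise a class, and a baseline walk that is high by chance makes a 15% fall easier to reach. Entry is restricted to Class III or IV, so that covariate has only two levels.

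The decision level is 0.05, where stated power is already 97%. The larger gains belong to the 0.01 sizing level or to the weaker 30% v 17% case.

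Adjustment is not quite free either. Missing baseline values need a rule, and the baseline walks follow randomization. They are blinded and pre-dose, so the risk of bias is small.

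What does not stand is the idea that weak covariates make adjustment harmful: with useless covariates the adjusted log-rank test showed no material loss. The subgroup analyses in SAP 6.15 are not a substitute for adjustment.

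**Conclusion.** This is a modest efficiency improvement to a valid analysis. The plan has no covariate-adjusted TtCW analysis of any kind, although the values are collected and already used elsewhere.

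Under the assumed SDs of 0.3, 0.5 and 0.7, with 113 events and 45% v 25%, power at 0.01 goes from about 88-89% to about 90-91%, 91-92% and 93-94%. At 0.05 the gain is about 1-2 points. At 30% v 17% and 0.05 it is about 1, 2 and 5 points. These sizes rest on the assumed prognostic strength and on log-linear covariate effects; opposing effects through the endpoint definition would shrink them.

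**What to change.** Before unblinding, amend SAP 6.12.6 so that the primary test is a covariate-adjusted log-rank test, stratified by treprostinil use, with three covariates: baseline average 6MWD, baseline WHO class (III v IV) and log NT-pro-BNP. Keep the unadjusted stratified log-rank test as supportive. At minimum, pre-specify the adjusted test as supportive.

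Keep the treprostinil-stratified Cox hazard ratio as the main estimate. If a covariate-adjusted Cox hazard ratio is also reported, label it as conditional.

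Fix the covariate list and a rule for missing baseline values in advance (for example, a missing indicator for NT-pro-BNP), and state that baseline 6MWD is taken after randomization, blinded and before first dose.

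The cost is wording: no patients, visits or assessments. Protocol section 10 lets statistical changes made before database lock be recorded in the SAP without a protocol amendment. The supportive option fits the addendum foreseen in SAP 6.12.8. Because SAP section 1 allows only minor changes after finalization, a change of primary test is cleaner as a revised SAP version.

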6.12.7 Supportive Analyses for Primary Analyses

Two distinct analyses will be performed for the components of the primary outcome.

1. “Contribution” outcome. A table will show the contribution of each component of the primary outcome.
2. “Incidence” outcome. Each component will be analyzed as a time-to-event variable.

These two analyses differ in that the analysis of the contribution shows only the first event in the primary outcome while the second considers the time to each component even if it is not the first event in the primary. For example, a subject who dies after experiencing disease progression would not show as a death in the analysis of the contribution of the component; however, the death of such a subject would be included in the second analysis.

Analysis of the “contribution” outcome will be descriptive. It will consist of a simple table showing the number of events of each type by treatment group contained in the primary outcome.

For the “incidence” outcomes, LIFETEST and PHREG will be used for each of the five individual components of the composite outcome. These analyses will use the component-specific dates of event or censoring. They will produce Kaplan-Meier curves, hazard ratios, 95% CIs, and other statistics as appropriate.

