1 INTRODUCTION

1.1 Pulmonary Arterial Hypertension Overview and Treatment

Pulmonary arterial hypertension (PAH), defined as an elevation in pulmonary arterial pressure and pulmonary vascular resistance, is a severe hemodynamic abnormality common to a variety of diseases and syndromes. Elevation in pulmonary arterial pressure causes an increase in right ventricular afterload, impairing right ventricular function and ultimately leading to heart failure and death.

The diagnosis of PAH requires confirmation with a right heart catheterization (RHC). The current hemodynamic definition of PAH is mean pulmonary artery pressure (PAPm) greater than 25 mmHg; a pulmonary capillary wedge pressure (PCWP), left atrial pressure, or left ventricular end-diastolic pressure (LVEDP) less than or equal to 15 mmHg; and a pulmonary vascular resistance (PVR) greater than 3 Wood units (McLaughlin et al, 2009).

Subjects most commonly present in their third and fourth decade; however, PAH may occur at any age. Women are more likely than men to be diagnosed with idiopathic PAH (McLaughin et al, 2009) (Rich et al, 2001). The prognosis of PAH is poor, with an approximately 15% mortality in the first year after diagnosis when treated with modern therapies (Thenappan et al, 2007).

The typical etiologies of PAH include idiopathic, heritable or associated with collagen vascular/connective tissue disease, portal hypertension, infection with the human immunodeficiency virus (HIV), history of cocaine inhalation and exposure to appetite suppressant drugs. An estimated annual incidence of approximately 2 cases per million has been reported for idiopathic PAH (Rich, 1987; Rubin 1997).

There are three major factors thought to contribute to the increased pulmonary vascular resistance seen in this disease: vasoconstriction, remodeling of the vessel wall, and thrombosis. There are a number of metabolic pathways which contribute to these changes that involve vasoactive mediators such as the vasodilators nitric oxide and prostacyclin, and the vasoconstrictor endothelin-1. These substances affect both vascular tone and remodeling leading to their use as pharmacologic targets (Farber, 2004).

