Initial start-up activities and recruitment of subjects will be restricted to ensure subject safety. As such, the sample size determination calculations will not include the initial 6 months of the study to make certain of adequate powering for this study. The accrual period and follow-up period used will be 1.5 and 2.5 years, respectively. Thus, assuming a one-year rate of clinical worsening of 45% in the placebo (inhaled treprostinil alone) group, 25% in the BPS-314*d*-MR group (a 20% reduction from inhaled treprostinil therapy alone), proportional hazards over time, an accrual period of 1.5 years, a 0.01 two-sided significance level, and a total follow-up time of 2.5 years, an exponential maximum likelihood test of equality of survival curves would require 113 events and 116 subjects per treatment group to detect treatment difference at a power of 90% at a 0.01 two-sided significance level (or 97% power at a 0.05 two-sided significance level or approximately 90% power at a 0.05 two-sided significance level to detect a 13% reduction from an inhaled treprostinil rate as low as 30%). Therefore, this study will randomize approximately 240 subjects. Sample size calculations were performed using nQuery Advisor 7.0 using sample size methods for the log-rank statistic based on Lakatos & Lan (1992). Subjects who discontinue from the trial will not be replaced.

The Sponsor will continuously monitor the overall (pooled) event and drop-out rates during the course of the study. Sample size may be increased during the trial to maintain the planned power at between 80% and 90% and the intended trial duration. Only pooled blinded data will be used to increase sample size.

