6.12.2 Hospitalization due to worsening PAH

Any hospitalization due to worsening PAH that occurs from randomization to the 30 days following subject's last study visit is counted as an event for the primary outcome. The date of the event is the actual date of hospitalization. All those without a reported hospitalization during the 30 days following their last visit are censored for hospitalization at the 30 day time even if it is known that they were hospitalized after the 30 day window.

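### Exploratory component analyses (SAP 6.12.7): death is ordinary censoring for the four non-fatal components, so Kaplan-Meier curves read as incidence run too high; the primary test is not affected

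*SAP*

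**What the plan says.** SAP 6.12.7 plans two views of the components. A contribution table counts, by treatment group, the first events that make up the composite. The incidence analyses then take each of the five components as its own time-to-event variable, whether or not it came first, using LIFETEST and PHREG with component-specific dates. Of the output the SAP says: "They will produce Kaplan-Meier curves, hazard ratios, 95% CIs, and other statistics as appropriate".

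SAP 6.12.6 gives each subject one of two things per component: an event date or a censoring date. There is no third state. For hospitalization, SAP 6.12.2 states: "All those without a reported hospitalization during the 30 days following their last visit are censored for hospitalization at the 30 day time". SAP 6.12.3 has the same rule for parenteral prostacyclin. SAP 6.12.4 and 6.12.5 censor progression and unsatisfactory response at the last study visit. None of the four sections says what happens to a subject who dies without the component. Neither document mentions competing risks or a cumulative incidence function.

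SAP 5.1.1 describes the component analyses as exploratory, and they lie outside the three testing stages of SAP 6.10. The only mortality figure in the documents is background: Protocol 1.1 cites "approximately 15% mortality in the first year after diagnosis".

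**The concern.** A subject who has died can no longer be hospitalized, start a parenteral prostacyclin or fail a walk test. For these components death is a competing event. Kaplan-Meier with death as censoring estimates the risk in a setting where nobody dies, on the assumption that those who died would have gone on to the event at the survivors' rate. Its complement is therefore higher than the share of subjects who actually have the event, and the gap grows with mortality and with follow-up.

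At stake is the absolute frequency of each non-fatal component by arm. A reader who takes the curves at their label would overstate it, and by different amounts in the two arms if mortality differs. The rules also leave a small gap in dates: a subject who dies 5 days after the last visit stays at risk of hospitalization until day 30.

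**Working it through.** **1. The plan's own figure.** No planned number is in dispute, but the design figures confirm the setting. The assumed one-year rates of 45% and 25% give HR = ln 0.75 / ln 0.55 = 0.481, with |ln HR| = 0.7315. By Schoenfeld's formula the events needed at two-sided 0.01 and 90% power are 4 × (2.576 + 1.282)² / 0.7315² = 111.2, so 112. SAP 4.1 says the test "would require 113 events overall to detect a treatment difference at a power of 90% at a 0.01 two-sided significance level", so the two agree to within one event. With 113 events, √113/2 × 0.7315 = 3.888. Subtracting 2.576 gives 1.312, or 90.5% power at 0.01. Subtracting 1.960 gives 1.928, or 97.3% at 0.05, which matches the stated 97%. An exponential maximum likelihood calculation with 1.5 years of accrual and 2.5 years in total gives 116.0 per arm, against 116 in Protocol 10.2.

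**2. Inputs for the component check.** The documents give no component rates and no trial mortality rate, so these are assumptions shown as ranges:
- component hazard h = 0.1, 0.2 or 0.3 per year;
- annual mortality 2%, 5%, 10% or 15%, where the last is the Protocol 1.1 figure held constant;
- death hazard d = −ln(1 − annual mortality) = 0.020, 0.051, 0.105 or 0.163 per year;
- constant, independent hazards; horizons of 1 and 2.5 years, the planned shortest and longest follow-up.

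**3. Formulas.** 1 − KM = 1 − exp(−h t). Cumulative incidence = h/(h + d) × [1 − exp(−(h + d) t)].

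Example: h = 0.2, mortality 15%, t = 2.5. 1 − KM = 1 − exp(−0.5) = 39.3%. Cumulative incidence = 0.2/0.3625 × [1 − exp(−0.906)] = 32.9%. The gap is 6.5 points.

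**4. Results at 2.5 years** (1 − KM is 22.1%, 39.3% and 52.8%; gaps are taken before rounding):

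| Annual mortality | Cumulative incidence, h = 0.1 / 0.2 / 0.3 | Overstatement, points |
|---|---|---|
| 2% | 21.6 / 38.4 / 51.6% | 0.5 / 0.9 / 1.1 |
| 5% | 20.8 / 37.1 / 49.9% | 1.3 / 2.2 / 2.8 |
| 10% | 19.5 / 35.0 / 47.1% | 2.6 / 4.4 / 5.6 |
| 15% | 18.3 / 32.9 / 44.5% | 3.8 / 6.5 / 8.3 |

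At 1 year the gap is 0.1 to 0.3 points at 2%, 0.2 to 0.6 at 5%, and 0.7 to 1.9 at 15%.

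**5. Plausibility of the upper corner.** One-year risk of death or the component is 1 − exp(−(h + d)). At 15% mortality this is 30.4% for h = 0.2 and 37.0% for h = 0.3. Both exceed the 25% that SAP 4.1 assumes for the whole composite on active treatment. With h = 0.3 and no deaths at all it is already 25.9%. These scenarios can describe the placebo arm at its planned 45%, but not the active arm as planned.

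**6. The SAP's own censoring rules, simulated.** With scheduled visits, follow-up of 1 to 2.5 years and a component rate of 25% in one year, the results at 2 years were:
- 10% annual mortality: 1 − KM of 43.9% under the 30-day rule and 44.0% under the last-visit rule, against a true 39.8%;
- 5% annual mortality: 43.8% and 43.6%, against a true 41.8%.

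The overstatement survives the rules as written. In principle, keeping dead subjects at risk to day 30 enlarges the risk set and lowers 1 − KM. In these runs the effect was too small to see.

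**7. What a cumulative incidence does between arms.** Take h = 0.2 in both arms, with annual mortality of 10% in one and 5% in the other. 1 − KM is 39.3% in both. The cumulative incidences at 2.5 years are 35.0% and 37.1%: the arm with fewer deaths has more component events because its subjects live to have them.

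**The case against.** The strongest reply is that little depends on these curves. They are exploratory by SAP 5.1.1 and outside the testing stages. The contribution table in the same section already shows which first events drive the composite, without any Kaplan-Meier estimate. The component log-rank and Cox results are valid as cause-specific comparisons when death is censored. All of this stands, and it limits the point to the absolute height of descriptive curves.

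The second reply concerns size. A reader might infer that 3.8 to 8.3 points is the error to expect at the trial's own mortality. The documents do not support that. The 15% refers to the first year after diagnosis in general, whereas this trial enrols established PAH after at least 90 days of inhaled treprostinil and excludes subjects expected to survive less than a year because of concomitant disease (Protocol 5.2 and 5.3). At 2% to 5% the gap is about 0.5 to 2.8 points.

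The third reply is that cumulative incidence is not a free improvement. As step 7 shows, it mixes in any mortality difference, and a drug that prolongs life can look worse on a non-fatal component. This also stands. It argues for showing the curve beside the cause-specific hazard ratio, not for leaving Kaplan-Meier as the only display of something called incidence.

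Two provisions might seem to cover the point already. The allowance for other statistics in 6.12.7 commits to nothing. The addenda in SAP 6.2 and 6.12.6 are announced for data conventions and for missing data in the primary outcome, and neither names this.

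**Conclusion.** The point holds as a limited one. For the four non-fatal components, 1 minus Kaplan-Meier read as incidence is too high once deaths precede later component events. The direction is certain. The size depends on a mortality rate that the documents do not give: under 2 points at 1 year, and at 2.5 years from about half a point (2% annual mortality, hazard 0.1) to about 8 points (15%, hazard 0.3), under constant independent hazards.

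The primary analysis counts death as an event and is unaffected. So are the death component and the testing hierarchy.

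Two stronger conclusions might be drawn and should not be. One is that the curves exaggerate the drug's non-fatal benefit: that presumes a mortality effect which is unknown, and depends on which quantity the reader wants. The other is that the 30-day rule adds to the overstatement: it works slightly the other way.

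**What to change.** In SAP 6.12.7, for the four non-fatal components, present Aalen-Johansen cumulative incidence curves by arm, with death as the competing event, as the display of absolute incidence. Keep the stratified Cox models and label their output as cause-specific hazard ratios. State that both are to be read beside the mortality result. Keep Kaplan-Meier for death and for the composite.

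In SAP 6.12.2 and 6.12.3, add that component censoring is no later than the date of death. Sections 6.12.4 and 6.12.5 need no such cap, because they censor at the last visit.

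No new data are needed. The cost is SAP wording, which the data-conventions addendum planned in SAP 6.2 could carry before unblinding, and minor programming. The interpretive cost is that cumulative incidence reflects any mortality difference between arms, so it must not be shown without the cause-specific hazard ratio.
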